##### **4.8.2 Adverse Events**

AEs will be coded using the Medical Dictionary for Regulatory Activities (MedDRA) Version 19.0.

Treatment-emergent adverse events (TEAEs) will be tabulated and are defined as those AEs that either start or worsen in severity on or after the date/time of first dose of study

treatment and on or before the final protocol required visit. In general, it is Week 18 Visit and 14 days after the date of last dose of study treatment.

Where dates are missing or partially missing, AEs will be assumed to be treatment-emergent, unless there is clear evidence (through comparison of partial dates) to suggest that the AE started prior to the first dose of study treatment or more than 14 days after the last dose of study treatment.

The AE will be summarized using MedDRA system organ class (SOC) and preferred term (PT). All AE summaries will provide the number of subjects reporting at least one AE and the total number of events reported. The following summaries will be provided:

- A summary of the number and percentage of subjects reporting at least one TEAE, drug-related TEAE, TEAE leading to withdrawal, serious adverse event (SAE), drug-related SAE, SAE leading to withdrawal and death by treatment group.
- A summary of the number and percentage of subjects reporting a TEAE by treatment group, SOC, and PT
- A summary of the number and percentage of subjects reporting a drug-related TEAE by treatment group, SOC, and PT
- A summary of the number and percentage of subjects reporting a treatment-emergent SAE by treatment group, SOC and PT
- A summary of the number and percentage of subjects reporting a drug-related treatment-emergent SAE by treatment group, SOC, and PT
- A summary of the number and percentage of subjects reporting a TEAE leading to withdrawal by treatment group, SOC, and PT
- A summary of the most common TEAEs by treatment group and PT (reported by >10% of subjects in any treatment group).
- A summary of the number and percentage of subjects reporting a TEAE by treatment group, severity, SOC and PT
- A summary of the number and percentage of subjects reporting a TEAE by treatment group, causality, SOC and PT

AE summaries will be ordered alphabetically for SOC, and PT within SOC.

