### 3 INVESTIGATIONAL PLAN

#### 3.1 Overall Study Design and Plan

[figure not shown]
This is a Phase 2, randomized, double-blind, placebo-controlled, dose-finding study to assess the efficacy, safety, tolerability, PK, and PD of orally administered vadadustat in Japanese subjects with anemia secondary to NDD-CKD.

The study has a planned enrollment of 48 subjects to be enrolled at approximately 25 sites in Japan. There will be 16 subjects in each of the 3 tablet-count groups.

An overview of the study design is presented in [Figure 1](#).

Figure 1: Overview of Study Design

\* For subjects who develop an excess Hb response during the primary efficacy period, the number of tablets of study drug will be decreased (see Section 8.2.4). For these subjects, the number of tablets of vadadustat initiated at the Week 6 visit will be lower than indicated.

The study will include the following periods:

- Eligibility screening period (up to 4 weeks)
- Primary efficacy period (6 weeks; Weeks 1 to 6)
- Dose adjustment and maintenance period (10 weeks; Weeks 7 to 16)
- Follow-up period (2 weeks; Weeks 17 and 18)

Subjects will participate in a screening period (4 days to 4 weeks) to determine study eligibility, and eligible subjects will be randomized following the screening period.

Using a central randomization system, subjects will be randomized 1:1:1 to receive 1, 2, or 4 tablets at their baseline visit (Day 1). Within each tablet-count group, subjects will be randomized 3:1 to receive vadadustat (150, 300, or 600 mg vadadustat) or placebo. See the protocol section 8.2.2 for information regarding the randomization scheme.

Study drug treatment will be administered during a 6-week primary efficacy period. See the protocol section 8.2.4 for information on study drug administration. The primary efficacy period includes fixed-dose treatment to establish a dose-response relationship. However, if Hb level increase rapidly or if the Hb level exceeds 13.0 g/dL, the study drug dose can be decreased or interrupted (see the protocol section 8.2.4).

After completing the primary efficacy period, subjects will continue to a 10-week dose adjustment and maintenance period (see the protocol section 8.2.5). Subjects receiving placebo will be switched to vadadustat, and study drug dose will be adjusted to achieve a target Hb of 10.0-12.0 g/dL based on dose adjustment guidelines (see the protocol section 8.2.5).

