##### **4.8.2 Adverse Events**

AEs will be coded using the Medical Dictionary for Regulatory Activities (MedDRA) Version 19.0.

Treatment-emergent adverse events (TEAEs) will be tabulated and are defined as those AEs that either start or worsen in severity on or after the date/time of first dose of study treatment and on or before the final protocol required visit. In general, it is Week 18 Visit and 14 days after the date of last dose of study treatment. The TEAEs are defined as those adverse events that started after first injection up to 14 days post-last dose.

Where dates are missing or partially missing, AEs will be assumed to be treatment-emergent, unless there is clear evidence (through comparison of partial dates) to suggest

that the AE started prior to the first dose of study treatment or more than 14 days after the last dose of study treatment.

Partial AE and concomitant medication start dates will be imputed as follows:

1. If the year (and month and day) is unknown, the date will be imputed as the date of first intake of study treatment if this is possible (i.e., the event end date is not prior to treatment start date).
2. If the month and day is unknown then:
  - a. If the year matches the first dose date, then impute the month and day of the first dose date.
  - b. If the year is earlier than the first dose date or the first dose date is not available (subject is not dosed) and matches the year of informed consent date, then impute the month and day of the informed consent date;
  - c. Otherwise, assign January 1.
3. If the day is unknown then:
  - a. If the month and year match the first dose date, then impute the day of the first dose date.
  - b. If the month and year are earlier than the first dose date or the first dose date is not available (subject is not dosed) and matches the month and year of the informed consent date, then impute the day of the informed consent date;
  - c. Otherwise, assign '1'.

Partial AE stop dates will be imputed as follows:

1. If the year is unknown, the date will not be imputed and will be assigned a missing value.
2. If the month is unknown, then assign December.
3. If the day is unknown, then assign the last day of the month.

For all other settings (eg. year missing, but day and month available etc.), imputation strategies will be reviewed and decided in the ongoing data cleaning and sponsor meetings.

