If the start and/or stop dates of medications other than study treatments are missing or partially missing, the dates will be compared as far as possible with the date of first study treatment administration.

If not specified, observed data approach will be performed.

The AE will be summarized using MedDRA system organ class (SOC) and preferred term (PT). All AE summaries will provide the number of subjects reporting at least one AE and the total number of events reported. The following summaries will be provided:

- A summary of the number and percentage of subjects reporting at least one TEAE, drug-related TEAE, TEAE leading to withdrawal, serious adverse event (SAE), drug-related SAE, SAE leading to withdrawal and death by treatment group.
- A summary of the number and percentage of subjects reporting a TEAE by treatment group, SOC, and PT
- A summary of the number and percentage of subjects reporting a drug-related TEAE by treatment group, SOC, and PT
- A summary of the number and percentage of subjects reporting a treatment-emergent SAE by treatment group, SOC and PT
- A summary of the number and percentage of subjects reporting a drug-related treatment-emergent SAE by treatment group, SOC, and PT
- A summary of the number and percentage of subjects reporting a drug-related TEAE leading to withdrawal by treatment group, SOC, and PT
- A summary of the number and percentage of subjects reporting a TEAE leading to withdrawal by treatment group, SOC, and PT
- A summary of the most common TEAEs by treatment group and PT (reported by >10% of subjects in any treatment group).
- A summary of the number and percentage of subjects reporting a TEAE by treatment group, severity, SOC and PT
- A summary of the number and percentage of subjects reporting a TEAE by treatment group, relationship, SOC and PT

AE summaries will be ordered alphabetically for SOC, and PT within SOC.

For each subject and each AE, the worst severity recorded will be attributed and used in the by-severity summaries. Similarly, the worst causality (most related to treatment) will be attributed and used in the by-causality summaries. If severity or causality is missing, data will be treated as observed

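### SAP section 4.8.2 defines treatment-emergent adverse events twice, with different content, and does not say which definition governs

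*SAP*

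**What the plan says.** The current SAP (Amendment 3) opens section 4.8.2 with a definition of TEAEs: they are "defined as those AEs that either start or worsen in severity on or after the date/time of first dose of study treatment", up to the final visit that the protocol requires. That end is then explained: "In general, it is Week 18 Visit and 14 days after the date of last dose of study treatment".

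The next sentence defines them again: "The TEAEs are defined as those adverse events that started after first injection up to 14 days post-last dose".

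The missing-date rule follows. It presumes an AE to be treatment-emergent unless partial dates clearly show "that the AE started prior to the first dose of study treatment or more than 14 days after the last dose of study treatment". Rules for imputing partial start dates come next. Rules 1, 2a and 3a set the start to the first-dose date, or to its month and day, when the known part of the date allows it.

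Three further statements bear on the reading:

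- Section 3.1 says that the study is to "assess the efficacy, safety, tolerability, PK, and PD of orally administered vadadustat in Japanese subjects".
- Later in section 4.8.2: "For each subject and each AE, the worst severity recorded will be attributed and used in the by-severity summaries".
- Section 4.8.2 of the original SAP has only the first definition ("Treatment-emergent adverse events (TEAEs) will be tabulated and are defined as those AEs that either start or worsen in severity"). The second sentence first appears in the next version and is still in the current one. The Amendment 3 change list touches section 4.8.2 only at the imputation of stop dates.

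**The concern.** A TEAE flag is one yes/no rule applied to every AE record, and most of the safety tables in section 4.8.2 are counts of that flag. Here the rule is given in two forms that classify some records differently, with no order of precedence. Two programmers working correctly from this SAP could deliver different tables, and a quality-control check against the text could not say which was right.

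The second sentence looks carried over from a trial of an injected product. It is nevertheless live text in the current plan, and it is the later of the two definitions on the page. If it is followed, the loss runs one way for worsening and for first-dose-date events: records drop out of the TEAE tables and none enter.

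**Working it through.** No sample size, error rate or model is involved, so the check sets the two definitions side by side and runs cases through them.

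| Element | First definition | Second definition |
|---|---|---|
| Qualifying event | Onset or increase in severity | Onset only |
| Window opens | On or after first dose | After first injection (no injection exists; read as first dose) |
| Window closes | Final required visit, explained as Week 18 and 14 days after last dose | 14 days after last dose |

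**Case 1: onset during screening, more severe on treatment, kept as one AE record.** First definition: counted. Second: not counted, because the start precedes dosing. The missing-date rule also tests the start only, so it does not bring worsening back. The worst-severity rule suggests that a single AE may carry more than one recorded severity, so this case can arise.

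**Case 2: AE dated to the first-dose date.** First definition: counted if it falls at or after dosing. Second, compared by date: not counted, because the first-dose date is not after itself.

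**Case 3: partial start date imputed under rule 1, 2a or 3a.** The imputed start equals the first-dose date. First definition: counted. Second, by date: not counted. This defeats the missing-date rule, which presumes such events to be emergent.

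**Case 4: end of window, completer.** Section 3.1 stops treatment at Week 16 and follows subjects for 2 weeks. Week 16 + 14 days = Week 18, so the two ends nominally coincide.

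**Case 5: end of window, early stopper.** Suppose, for illustration, that the last dose falls at Week 4. Then 14 days after last dose is Week 6. If the first definition is held to the Week 18 visit, its window runs 18 − 6 = 12 weeks longer. If its final required visit is an earlier withdrawal visit, the gap shrinks or reverses. The explanation joins Week 18 and 14 days with a bare conjunction, so the ambiguity sits partly inside the first definition.

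**Which outputs carry the flag.** Section 4.8.2 lists ten AE summaries. Nine are restricted to TEAEs or treatment-emergent SAEs. The tenth, the overview, is restricted for its TEAE counts but not for its SAE and death counts. The all-AE listing, the screening SAE table and the death summaries in section 4.8.3 carry no treatment-emergent restriction, and the special-interest summaries are worded as AEs.

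**Granularity.** Section 4.10 plans 12 subjects per group, so one reclassified subject moves a group rate by 1/12 = 8.3 percentage points. In the common-event table, with its cut at more than 10%, 1/12 = 8.3% is left out and 2/12 = 16.7% is shown. This shows how sensitive the tables are; it does not estimate how many subjects would move.

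**The case against.** The case for leaving this alone, or calling it editorial, has several parts.

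*Recording convention.* If the protocol or eCRF opens a new AE record, with its own onset date, whenever a condition worsens, the second definition captures the worsening anyway. Chronic conditions belong to medical history, and their worsening on treatment may well be entered as a new event. Section 4.8.5.1 points that way for vital signs by treating emergent abnormalities as adverse events. This stands as a limit on size. It is not a resolution, because this SAP states no such convention.

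*First-dose boundary.* The missing-date and imputation rules both favour counting from the first-dose date. That is a fair reading of intent, but it makes the second sentence inconsistent with its own paragraph.

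*End of window.* For completers there is no practical difference. This stands; only early discontinuation leaves a question.

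*Reach.* A reader might infer that every AE table rests on this flag, and that the second sentence would strip worsened hypertension or hyperkalaemia from the special-interest signal. The SAP does not support that. The special-interest summaries are specified for AEs, with no statement that they are restricted to TEAEs, and the outputs without the flag are noted above. Blood pressure and potassium also have analyses that do not use the AE flag, in sections 4.8.4.7, 4.8.5.1 and 4.9.2.

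*Importance.* AE summaries are descriptive, and no efficacy conclusion depends on them. This is true, and it sets the priority. It does not remove the contradiction.

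**Conclusion.** Wrong as written. The two definitions differ on whether worsening counts and on whether the first-dose date is inside the window; for early stoppers the end of the window is also unsettled. The document gives no rule for choosing between them.

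The consequence is confined to the TEAE and treatment-emergent SAE tables in section 4.8.2 and the TEAE counts of the overview. How many events would move cannot be computed: it depends on how the eCRF records worsening, on how many records start before or on the first-dose date, and on how many subjects stop early. The conclusion rests on a literal reading of the second sentence with injection taken to mean first dose, and on comparison by date for first-dose-date events. The primary efficacy result is untouched. It should be corrected because the correction is cheap and the flag feeds most of the AE tables.

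**What to change.** 1. Delete the second definition and keep one. An AE is treatment-emergent if it begins, or increases in severity, on or after the first dose of study drug and no later than a single stated end of window.
2. Choose that end explicitly and apply it to completers and early stoppers alike. Fourteen days after last dose is one option; the missing-date rule already uses it.
3. Amend the missing-date rule so that an AE known to have started before the first dose, but to have worsened in severity on treatment, is still counted. At present the rule looks only at when the event started.

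The cost is one deleted sentence, matching edits to the retained definition and the missing-date rule, and one derived flag in the programs. If any TEAE tables have already been produced under the second definition, they would need to be rerun. No new data are needed if the eCRF already allows worsening to be identified.

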#### 4.5 Demographic and Other Baseline Characteristics

The demographic and other baseline characteristics will be summarized for the MITT and safety populations. The following summaries will be provided:

- A summary of demographic variables (e.g. age, gender, weight, height and body mass index [BMI]) by treatment group and all subjects

- A summary of other relevant variables (e.g. estimated Glomerular Filtration Rate [eGFR] at baseline, CKD stage, etiology of CKD and smoking status) by treatment group and all subjects
- A summary of relevant medical history by treatment group and all subjects.
- A summary of prior and concomitant medications within 30 days prior to the first study drug dose up to and including Week 6 by treatment group and overall.
- For the final analysis, a summary of concomitant medications after Week 6 will be provided.

Age will be calculated as the number of complete years between a subject's birth date and the date of informed consent.

Definitions of eGFR and CKD stage are described in [section 4.8.4.7](#).

CKD stage will be determined by eGFR at baseline:

CKD stage	eGFR (mL/min/1.73m  )
1	90+
2	60 - 89
3a	45 - 59
3b	30 - 44
4	15 - 29
5	< 15

By-subject listings of demographic data and other baseline characteristics (as summarized above) will be provided

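### SAP 4.8.2: start-date rules 2a and 3a impute the first-dose date without rule 1's stop-date check, so a record that ended before treatment can be given a start after its own stop

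*SAP*

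**What the plan says.** The text is in SAP section 4.8.2 (Adverse Events), as it stands after Amendment 3. The scope covers both record types: "Partial AE and concomitant medication start dates will be imputed as follows".

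- **Rule 1**, whole start date unknown: use the first-dose date, provided that "the event end date is not prior to treatment start date".
- **Rule 2a**, month and day unknown: "If the year matches the first dose date, then impute the month and day of the first dose date".
- **Rule 3a**, day unknown: "If the month and year match the first dose date, then impute the day of the first dose date".

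Rules 2b and 3b use the informed consent date for partial dates that are earlier than first dose and match the consent year, or the consent month and year.

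Two other sentences in the section bear on the same records. For events with missing or partial dates, "AEs will be assumed to be treatment-emergent, unless there is clear evidence (through comparison of partial dates) to suggest" a start before first dose or more than 14 days after last dose. For medications with missing or partial dates, "the dates will be compared as far as possible with the date of first study treatment administration".

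**The concern.** Rule 1 shows that the authors saw the hazard: first dose is not a credible start for something that had already stopped. The check appears in only one of the three branches that assign the first-dose date. In the other two, a recorded stop before treatment is ignored and the record acquires an impossible order of dates.

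Three kinds of output are exposed:

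- The adverse event listing in section 4.8.2 prints onset, resolution and duration, so the impossible order would be visible there if imputed dates are used.
- Treatment-emergent status depends on whether the program uses the imputed start or the clear-evidence sentence.
- A medication that ended before treatment, including an erythropoiesis-stimulating agent (ESA), can be dated to Day 1. It can then enter on-treatment summaries, or the from-baseline ESA administration count in section 4.7.3, if these are derived from the imputed start.

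**Working it through.** The plan gives no figure to reproduce here. The check applies the rules literally to example dates.

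**Inputs.** The rules are those of section 4.8.2. The dates are assumptions: consent 1 March 2017, first dose 22 March 2017. The SAP gives no formula for event duration, so I use stop - start + 1, the form that section 4.8.1 uses for treatment duration.

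| Recorded start | Recorded stop | Rule | Imputed start | Duration (days) |
|---|---|---|---|---|
| fully unknown | 12 Mar 2017 | 1 | first-dose date blocked | none |
| 2017 | 12 Mar 2017 | 2a | 22 Mar 2017 | 12 - 22 + 1 = -9 |
| Mar 2017 | 12 Mar 2017 | 3a | 22 Mar 2017 | 12 - 22 + 1 = -9 |
| 2017 | Feb 2017 | 2a | 22 Mar 2017 | at the latest possible stop, 28 Feb: -22 + 1 = -21 |
| Mar 2017 | 30 Mar 2017 | 3a | 22 Mar 2017 | 30 - 22 + 1 = 9 |

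The first three rows share a stop date. Rule 1, with the least information about the start, handles it properly; rules 2a and 3a, with more, produce a start ten days after the stop. The last row shows that the rules work as intended when the stop falls on or after first dose.

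**Reach of each rule.** Rule 3a needs a missing day and a known month equal to the first-dose month. With screening of S days and first dose on day d of the month, the screening days it can misdate number min(S, d - 1). Section 3.1 sets screening at 4 days to 4 weeks. The count is therefore 0 for dosing on the 1st and at most min(28, 30) = 28 for dosing on the 31st. Rule 2a needs both month and day missing, and then reaches any earlier date in the first-dose year. In either case harm arises only if the recorded stop precedes first dose.

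**Do the other sentences settle it?**

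- *Adverse events.* A stop before first dose is clear evidence of an earlier start, so the clear-evidence sentence makes the event not treatment-emergent. The start imputed under 2a or 3a makes it treatment-emergent. No order of precedence is given, and the sentence governs status only: it does not alter the imputed date.
- *Medications.* The section requires a comparison with first dose but states no action when the stop is earlier, and no override of 2a or 3a.
- *Other date patterns.* Section 4.8.2 leaves unlisted patterns to data-cleaning and sponsor meetings. The patterns in 2a and 3a are listed, so that provision does not reach them.

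**The case against.** The strongest reply is that the SAP already contains the remedy. In every pre-treatment example above the clear-evidence sentence points to the right status, and a careful programmer would follow it. That largely stands for adverse events. A reader might infer that screening events will inflate the treatment-emergent counts. The SAP does not support that; it supports only that they can be counted, depending on an unstated precedence.

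The medication consequences are also narrower than they may look. Section 4.5 plans one combined table: "A summary of prior and concomitant medications within 30 days prior to the first study drug dose up to and including Week 6". A drug stopped within those 30 days belongs there whatever its imputed start. Only one that ended more than 30 days before dosing could enter wrongly, and only if its stop date is ignored. ESA rescue in section 4.7.3 requires four criteria at once, so a misdated start alone cannot create a rescue. The separate ESA administration count has no such filter and remains exposed.

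Two further inferences should be resisted. One is a percentage-point shift per arm: the SAP gives no count of partial dates, so any such range would rest on an invented number. The other is that stop-date imputation for medications, which Amendment 3 removed, should be restored. Those rules assign the latest possible date, so a stop recorded as March 2017 would become 31 March and could hide a stop before 22 March. Where a partial stop is decisive, comparing its known parts with the first-dose date is enough.

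What survives is that the rules, as written, yield an impossible date, and that nothing in the section says what date to use instead.

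**Conclusion.** The point holds as a minor but definite defect in a stated rule. Rules 2a and 3a omit a condition that rule 1 contains, and literal application gives a start after the stop for any event or medication that has a matching partial start and a stop before first dose.

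For adverse events, the effect on treatment-emergent status is possible but not certain. For medications, a Day 1 start for a treatment already ended can reach on-treatment or from-baseline counts if these use the imputed start. The number of affected records cannot be known from the SAP and may be zero. The primary haemoglobin analysis does not use these dates and is untouched. The worked durations rest on assumed consent, dosing and stop dates, but the ordering error does not depend on the particular dates chosen.

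**What to change.** 1. Add to rules 2a and 3a: impute the first-dose date only if the recorded stop date (complete, or its known parts) is not before the first-dose date. Otherwise impute the informed consent date, if it matches the recorded parts and is not after the stop. Failing that, impute the earliest date consistent with the recorded parts. Classify the record as pre-treatment.
2. State that the clear-evidence sentence takes precedence over the imputed date in deciding treatment-emergent status.

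Using the consent date first keeps to the convention of rules 2b and 3b. In the examples, both records stopping on 12 March would start on 1 March (duration 12 - 1 + 1 = 12). The record stopping in February would start on 1 January, because consent on 1 March falls after its stop. The record stopping on 30 March keeps its start of 22 March and duration of 9, as would any record whose stop is not shown to precede first dose.

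The cost is a few lines of SAP text and one condition in the date-derivation program. The one side effect is that the last fallback can place a start before consent, as in the February example; it applies only when the consent date does not fit the recorded parts or falls after the stop.

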### 2.2 Secondary Objectives and Endpoints

The secondary objectives of this study are:

- To assess the safety, tolerability, pharmacokinetics (PK), and pharmacodynamics (PD) of oral vadadustat once daily dosing in Japanese subjects with anemia secondary to NDD-CKD during the 6-week, primary efficacy period
- To evaluate the effect of dose adjustments and demonstrate the maintenance effect on Hb during a 10-week dose-adjustment and maintenance period
- To assess the time to reach the target Hb range from baseline

The efficacy endpoints that will be used to assess these objectives include the following:

- Time to reach target Hb level of 10.0-12.0 g/dL from baseline visit (Day 1)
- Mean Hb levels at the end of the primary efficacy period (Week 6) and at the end of the dose adjustment and maintenance period (Week 16)
- Proportion of subjects who achieve target Hb 10.0-12.0 g/dL at the end of the dose adjustment and maintenance period (Week 16)
- Mean change in Hb between pre-treatment and the end of the dose adjustment and maintenance period (Week 16)
- Mean change in hematocrit, red blood cell (RBC) count, and reticulocyte count from baseline to the end of the primary efficacy period (Week 6) and the end of the dose adjustment and maintenance period (Week 16)
- Mean change in iron indices (ie, iron, total iron-binding capacity [TIBC], transferrin saturation [TSAT], and ferritin) and hepcidin from baseline to the end of the primary efficacy period (Week 6) and the end of the dose adjustment and maintenance period (Week 16)
- Proportion of subjects requiring rescue with RBC transfusion from baseline to the end of the primary efficacy period (Week 6) and the end of the dose adjustment and maintenance period (Week 16)
- Proportion of subjects requiring rescue with ESAs from baseline to the end of the primary efficacy period (Week 6) and the end of the dose adjustment and maintenance period (Week 16)
- Number of dose adjustments from baseline to the end of the dose adjustment and maintenance period (Week 16)
- Maintenance of iron sufficiency (defined as ferritin  $\geq 50$  ng/mL and TSAT  $\geq 20\%$ ) from baseline to the end of the primary efficacy period (Week 6) and the end of the dose adjustment and maintenance period (Week 16)
- Plasma concentration profile of vadadustat and its metabolites using pre-dose sample from Week 4

The safety endpoints that will be used to assess these objectives include the following:

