#### 4.7.1.5 Preliminary (6-Week) Analysis

After all subject performed assessment of the Week 6 Visit, preliminary analysis will be performed. As the study conduct and final analysis will not be modified by this analysis, no alpha adjustment is proposed. It is expected that this 6-week data will be identical for the preliminary analysis and the final analysis of the complete dataset. Any changes between the preliminary analysis and the final analysis will be documented. The preliminary analysis will be performed by the independent unblinded team. All data through the cutoff date of the last subject randomized who completes week 6 will be analyzed. Blinding of blinded team and investigators will be maintained to prevent potential bias.

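### TEAE, SAE, withdrawal and death tables use one whole-study window by treatment group, so as written the placebo column mixes 6 weeks of placebo with 10 weeks of vadadustat

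*SAP*

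**What the plan says.** All references are to the current SAP text (Amendment 3).

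- **Switch (3.1).** After the primary efficacy period, "Subjects receiving placebo will be switched to vadadustat, and study drug dose will be adjusted to achieve a target Hb of 10.0-12.0 g/dL". The primary efficacy period is Weeks 1 to 6, dose adjustment and maintenance is Weeks 7 to 16, and follow-up is Weeks 17 and 18.
- **Safety objective (2.2).** Safety and tolerability are to be assessed for "oral vadadustat once daily dosing in Japanese subjects with anemia secondary to NDD-CKD during the 6-week, primary efficacy period".
- **AE window (4.8.2).** A TEAE starts or worsens from first dose up to the final required visit, in general Week 18 and 14 days after last dose. This is one window for the whole study.
- **AE tables (4.8.2, 4.8.3).** The typical layout is "A summary of the number and percentage of subjects reporting a TEAE by treatment group, SOC, and PT". The drug-related, serious and withdrawal tables, and the death tables in 4.8.3, are also by treatment group with no period.
- **Special-interest AEs (4.8.2).** Counts and percentages are promised, but neither treatment group nor period is stated.
- **Grouping (4.4.1).** The safety population is analysed as treated, by allocated group. Nothing is said about the group of a placebo subject after the switch.
- **Preliminary analysis (4.7.1.5).** "All data through the cutoff date of the last subject randomized who completes week 6 will be analyzed".

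**The concern.** Take a placebo subject with an event in Week 10. The subject is then on vadadustat, the event lies inside the TEAE window, and the only column the tables offer is the subject's allocated group, placebo. Events arising on active drug therefore raise the placebo rate, which pulls any excess on vadadustat towards no difference. In a safety table that error hides harm.

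Weeks 1 to 6 are the only period with a concurrent placebo arm and nominally fixed doses, and they are the period named in the safety objective. Yet no AE, SAE, withdrawal or death table is specified for them.

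The SAP recognises the Week 6 boundary elsewhere. Disposition (4.3.1) and concomitant medications (4.5) are divided at Week 6. Protocol deviations (4.3.2) and the blood pressure, heart rate and potassium outliers (4.9.2) are split by period. The AE tables are not.

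**Working it through.** The SAP states no AE rate, so it has no figure of its own to reproduce here. The check uses its period lengths and group size, then an illustration with assumed rates.

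**1. What the placebo column contains.** Inputs: 6 weeks before and 10 weeks after the switch (3.1), and 12 placebo subjects (4.10), all assumed to complete.

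- Placebo time: 12 × 6 = 72 subject-weeks.
- Vadadustat time: 12 × 10 = 120 subject-weeks.
- Share on vadadustat: 120 / 192 = 10/16 = 62.5%.
- Share of the 18-week TEAE window after the switch: 12/18 = 66.7%.

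**2. Effect on a rate ratio (assumed true ratio r).** Over 16 weeks the active column has rate 16r and the placebo column 6 + 10r, in units of the placebo rate. The ratio shown is 16r / (6 + 10r).

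- r = 1.5: 24/21 = 1.14
- r = 2: 32/26 = 1.23
- r = 3: 48/36 = 1.33

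**3. Effect on the proportion with an event, separating the switch from longer follow-up.** Let p and d be the assumed 6-week risks on placebo and vadadustat, with constant weekly hazards hp = −ln(1−p)/6 and hd = −ln(1−d)/6. Risks to Week 16:

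- Active: 1 − exp(−16hd)
- Placebo column without a switch: 1 − exp(−16hp)
- Placebo column as planned: 1 − exp(−(6hp + 10hd))

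For p = 10% and d = 25%, 6hp = 0.1054 and 6hd = 0.2877.

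- Active: 1 − exp(−0.7672) = 53.6%
- Placebo, no switch: 1 − exp(−0.2810) = 24.5%, ratio 2.19
- Placebo, as planned: 1 − exp(−(0.1054 + 0.4795)) = 44.3%, ratio 1.21

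| Assumed 6-week risks | Ratio at Week 6 | Week 16 ratio, no switch | Week 16 ratio, as planned |
|---|---|---|---|
| 10% vs 25% | 2.5 | 2.19 | 1.21 |
| 5% vs 20% | 4.0 | 3.51 | 1.30 |
| 10% vs 40% | 4.0 | 3.04 | 1.21 |

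The effect of the switch is the step from the third column to the fourth. The step from the second to the third is cumulative risk saturating over longer follow-up, which would occur anyway.

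**The case against.** Several stronger statements are tempting, and the SAP does not support them.

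- **That exposure has no split.** Section 4.8.1 gives treatment duration by group and study visit, and 4.7.3 gives average daily dose by group and visit. What remains is that duration from first to last administration does not separate placebo time from vadadustat time.
- **That all these tables are by randomised group.** Section 4.4.1 says as treated, by allocated group. The two coincide only when allocation is correct. The special-interest summaries name no group, so they are under-specified. Counting later events under placebo follows from the table layout and the missing rule; it is not a stated rule.
- **That the placebo-controlled safety comparison is lost.** It survives for blood counts, chemistry and vital signs by time point, for CRP and VEGF with a Week 6 ANCOVA, for liver abnormalities by visit, and for the outlier analysis by period. AE onset dates are listed, so Weeks 1 to 6 events can be recovered.
- **That the AE tables determine the Phase 3 starting dose.** Section 2.1 ties that choice to the Hb dose-response; safety is a secondary objective.
- **That the switch explains a fall from 2.5 to 1.21.** Part of that fall is the saturation shown above.

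Two defences deserve an answer. First, 4.7.1.5 is titled a 6-week analysis and expects its 6-week data to be identical in the preliminary and final analyses, which suggests a distinct 6-week data set. Its cutoff, however, is a calendar date, so read literally early enrollees bring post-switch events. The scope is ambiguous, and the section cannot be relied on to supply a clean 6-week AE table. Second, table shells exist (5.1.1.1 mentions them) and may carry period columns. They are not shown, and the SAP text that governs the tables has none. Listings with onset dates allow a later split, but not a pre-specified one.

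**Conclusion.** The point stands for the TEAE, SAE, withdrawal and death tables, and as under-specification for the special-interest AE summaries. As written, 62.5% of treatment time in the placebo column is on vadadustat, no rule attributes former placebo subjects' later events, and no AE table matches the 6-week safety objective. The 62.5% rests only on the SAP's period lengths and on completion of treatment.

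The size of the dilution rests on assumed event rates and constant hazards, and ignores that doses in the active arms are also adjusted after Week 6. Under those assumptions the switch takes a Week 16 risk ratio of 2.19 down to 1.21, and true rate ratios of 1.5 to 3 appear as 1.14 to 1.33. The direction is towards understating a difference. The fault lies in the AE summary specification and can be repaired from data already collected.

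**What to change.** 1. **Sections 4.8.2 and 4.8.3.** Produce the TEAE, SAE, special-interest AE, withdrawal and death tables separately for (a) first dose up to each subject's own Week 6 switch, by the four arms, and (b) after the switch to 14 days after last dose, with former placebo subjects in their own 'placebo to vadadustat' column. Assign each event by its date of onset or worsening. State group and period for the special-interest summaries.
2. **Section 4.8.1.** For former placebo subjects, report placebo duration and vadadustat duration separately.
3. **Section 4.7.1.5.** Cut the 6-week safety tables at each subject's own Week 6 visit, not at a common calendar date.

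The cost is SAP wording, one period flag in the AE dataset and about twice as many AE tables. No new data are needed.
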